## 5.3 Therapy failure

Treatment failure is defined as any reported worsening in the PGI-I questionnaire at the end of the study or the start of any interventions against the incontinence symptoms (conservative and invasive methods).

Kranus Health GmbH\_DINKS

## 6 Study design and description

### 6.1 Type of study, therapy allocation, scope of the study

This is a single-blind, two-arm, randomised study with an intervention and a control group. The study is being conducted at Mainz University Hospital and recruitment is taking place throughout Germany. A total of 198 patients will be included, 99 in the intervention group and 99 in the control group.

### 6.2 Patient recruitment

The study centre is a urological university clinic. Patients recruited via the study centre as well as via urological, general practitioner or gynaecological outpatient clinics and practices throughout Germany and via direct contact with affected patients.

### 6.3 Timetable

Recruitment phase: 01.04.2024 to 31.10.2024 Study start:

with positive ethics vote (FPI) Treatment duration: 12 weeks.

End of studies: 15 February 2025 (LPO)

[figure not shown]
Final report: by 15 April 2025

### 6.4 Study centre

The responsible study centre is the Urological University Clinic Mainz. The centre receives training on the study and the corresponding information and training documents. The training is documented in writing. The centre receives the complete study documents.

### 6.5 Study programme

The study will be recruited via the Kranus Health GmbH network of gynaecologists, general practitioners and urologists, by directly approaching patients, a study landing page and, if necessary, online advertising. **Figure 1** outlines the study process.

*Figure 1: Study flow chart*

The end of the programme is planned for 12 weeks after LPI.

## 6.6 Patient insurance

During the study, all study participants are insured in accordance with the applicable law. According to the General Terms and Conditions of Insurance, the insurance cover extends to all damage to health that occurs as a result of the study during and after participation. Only financial disadvantage is covered; no compensation for pain and suffering is paid.

## 6.7 Screening, information and consent

The initial screening of patients takes place via the study portal and urological, gynaecological and general medical practices. If patients are interested in participating in the study, they register in the study tool (Dacima from Evident IQ, information on data security and compliance of the server structure is provided in accordance with ISO27001 and specified in the other documents attached to the submission) and are assigned a patient ID. The study centre in Mainz will check the inclusion and exclusion criteria and, if necessary, subsequently inform the patients. The study participant will be informed about the nature, significance, objectives, possible risks, expected benefits, scope and other aspects of the study.

After the information session, each patient is given sufficient time and opportunity to clarify any unanswered questions and decide whether to participate.

Each eligible patient signs and dates her consent to participate in the study, voluntarily, in person on the consent form online or by hand. The patient's consent also expressly refers to the collection and processing of personal data.

Kranus Health GmbH\_DINKS

data. Patients are therefore explicitly informed about the purpose and scope of the collection and use of this data, in particular health data.

One copy of the signed consent form (copy or 2nd original) remains with the patient or is sent by email, the other in electronic form on the study server, to which only the study centre has access.

The patient can withdraw consent at any time and without giving reasons and discontinue treatment or end the study. In such cases, the patient is asked to state the reason for withdrawal (for treatment or participation), but is advised that she does not have to do so. The time of withdrawal of the declaration of consent for the study must be documented.

The patient information and consent form is a separate document to this study protocol.

Patients for whom it becomes apparent during the informed consent discussion with the study centre that they do not meet an inclusion criterion, meet an exclusion criterion or for whom it becomes apparent after signing the informed consent form that they do not meet the eligibility criteria for participation in the study are assessed and documented as screening failures.

## 6.8 Pre-screening, medical history, inclusion procedure

In the first step, the prospective patient registers via the study portal and fills out a few questions to initially check potential eligibility based on the inclusion and exclusion criteria. If the result of the check is positive, the patient registers in Evident IQ's Dacima study tool, receives a patient ID, fills out a medical history form and provides proof of diagnosis. If the criteria are met, an appointment is made with the study centre, which checks the inclusion and exclusion criteria again. The patient is then informed about the study and can ask questions about the study and its procedure. Once the consent form has signed voluntarily and independently, the patient is included in the study.

Essential basic information (study centre, date of consent, year of birth, age, gender, inclusion/exclusion criteria, etc.) is stored in the eCRF. All patients record their incontinence episodes over a period of three days (3 x 24 h). The baseline data collection then takes place in the study tool, followed by randomisation to the respective study arm in the study tool. For documentation purposes, a form on the randomisation result (block randomisation 1:1) is generated via the study tool. Furthermore, the intervention patients fill out a micturition diary in the app to record micturition frequency, drinking volume and other symptoms.

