1.5 Business round scheme

Table 1: Visit scheme for the DINKS study

	Study implementation / treatment phase							Follow Up			
	Before enrolment/ pre-screening	Inclusion	Baseline/telephone V1 week 1*	Onboarding IG/ after study inclusion	Technical support call week 2	V2 Week 6*	End of study Telephone V3 week 12*	Onboarding KG/IG	Follow-up questionnaire week 24* (IG, KG)	Follow-up questionnaire week 36* (IG, KG)	Follow-up questionnaire week 48* (IG, KG)
Medical history/basic data collection	X	X									
Stress-Urge-Incontinence-questionnaire (S/U-IQ)			X				X		X	X	X
Verification of input and output Exclusion criteria	X	X									
Clarification, Declaration of consent		X									
Randomisation			X								
Questionnaires (I-QOL and ICIQ-UI-SF)			X				X		X	X	X
PGI-I							X		X	X	X
Technical support				X (IG)	X (IG)			X			
Micturition diary				X (ongoing documentation possible)		X	X	X	X	X	X
Incontinence documentation over 72h		X					X		X	X	X
Acquisition (new) Concomitant medication/therapies	X	X	X			X	X		X	X	X
Recording of adverse events**		X	X	X	X	Additional telephone enquiry	X	X	X	X	X

\*Week +/-7 d

\*\*IA/SAE/Incidentes via SZ, by telephone ([contact]) or by e-mail[[contact]](mailto:[contact]) IG:

Intervention group

KG: Control group

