### 3 Test population

#### 3.1 Inclusion criteria

- ICD-10 codes:  
N39.3 Stress incontinence N39.42 Urge incontinence  
Mixed incontinence
- Persons with urge incontinence who were assigned to the female sex at birth, Stress incontinence, mixed incontinence (IE≥ 1 per day)
- Age≥ 18 years
- Mastery of the German language
- Internet access
- Tablet or smartphone access (Android not older than version 7 and iPhone not older than iPhone 9)
- Informed consent: written consent of the participating patients

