### 8.2 Primary endpoint

- 1) Relative change (rel-CfB-IEF) of the IEF from baseline to week 12 in relation to baseline

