### 8.3 Secondary endpoints

- 2) Change in ICIQ-SF from baseline to week 12
- 3) Change in I-QOL from baseline to week 12
- 4) Change in the PAM-13 questionnaire from baseline to week 12
- 5) PGI-I questionnaire (overall improvement after treatment) at the end of the study
- 6) Proportion of patients without incontinence (cured patients) at the end of the study
- 7) Reduction in micturition frequency during the day
- 8) Reduction in micturition frequency at night
- 9) Reduction in pad consumption
- 10) Reduction of the imperative urge to urinate
- 11) Change in functional bladder capacity
- 12) Reduction in body weight
- 13) Reduction in the proportion of patients with treatment failure within the study period
- 14) Proportion of patients with at least 50% reduction in IEF from baseline to week 12
- 15) Reduction in the frequency of stress incontinence episodes in the S/U-IQ
- 16) Reduction in the frequency of urge incontinence episodes in the S/U-IQ

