## 8.6 Primary endpoint

There is no standardised method for measuring incontinence episodes. In a study very similar to ours (app-based pelvic floor muscle training for stress incontinence), the incontinence episodes were measured in the micturition diary on 2 days and then multiplied by 3.5 to obtain a weekly average [8]. In a similar, internet-based pelvic floor training study, Sjöström et al. used an analogue measurement system [33]. In a study with different conservative measures (including pelvic floor muscle training), Bo et al. the incontinence episodes over 3 days [34]. Castro et al [35] measured incontinence episodes over 7 days in a similar study.

In the present study, incontinence episodes were measured over 3 days (baseline and end-of-study), the mean value per day was calculated and this was used as the primary endpoint.

There is a lack of data in the literature on the minimum clinically relevant difference (MID) in connection with specific measures such as medication or pelvic floor muscle training. In general, a reduction of 50% is described as clinically relevant for conservative measures for incontinence [6, 31]. Based on the literature, we define a reduction in incontinence episodes as the quantitative primary endpoint.

Statistically analysed is primarily the relative change ( $rel-CfB-IEF = CfB/B$ ) of the IEF from baseline to week 12 in relation to baseline; desired reduction of the mean relative IEF by 50% versus control; IEF frequency = mean value of IEs over 24 hours calculated from IEs over 72 hours.

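### Does the plan need an entry check and a special rule for women whose baseline 72-hour record shows no, or very few, incontinence episodes?

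*Combined protocol and SAP*

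**What the plan says.** The entry threshold stands in section 3.1 as "mixed incontinence (IE≥ 1 per day"), with no instrument, time window or averaging rule. Section 6.8 describes eligibility checks by the portal and the study centre, then consent, after which "the patient is included in the study". It then says "All patients record their incontinence episodes over a period of three days (3 x 24 h"), followed by baseline data collection and randomisation.

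Two other places bear on the order. In Table 1 (section 1.5) the row "Incontinence documentation over 72h" has its first mark in the Inclusion column. The check of the entry criteria is also marked there, and randomisation comes in the next column, Baseline/V1. Section 6.7 treats patients "for whom it becomes apparent after signing the informed consent form that they do not meet the eligibility criteria" as screening failures.

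The primary endpoint (section 8.2) is "Relative change (rel-CfB-IEF) of the IEF from baseline to week 12 in relation to baseline", with IEF taken from the 72-hour record (sections 5.1 and 8.6). Endpoint 14 (section 8.3) is "Proportion of patients with at least 50% reduction in IEF from baseline to week 12". Section 8.8 defines the Full Analysis Set (FAS) as the randomised women except those who withdraw consent at once. It imputes missing values of endpoints 1 to 4 by jump-to-reference and adds a Wilcoxon test as a sensitivity analysis. Section 8.12 announces a detailed SAP before evaluation; it is not among the documents.

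**The concern.** Read alone, section 6.8 puts the eligibility decision before the 72-hour record and describes no check between the record and randomisation. A woman who reports daily leakage but records zero to two episodes in three days could then be randomised.

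Two consequences would follow. With a record of zero, endpoints 1 and 14 cannot be calculated although both counts were observed. The imputation rule covers missing values, not a division by zero, so dropping the woman, imputing her or assigning a value would all stay open. With one or two episodes, chance in the denominator makes the ratio erratic: from a baseline of one, one extra episode is +100%; from a baseline of three, it is +33%. That raises the variance and pulls the mean ratio upward. Since the primary endpoint opens the fixed test sequence for endpoints 2 to 4, a choice made after seeing results, or a distorted estimate set against the 50% aim, would matter.

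**Working it through.** **1. The plan's own figure.** Section 8.4 gives d/s = 0.7, two-sided alpha 5% and power 90%, with 2 × 44 = 88. The t-test calculation gives 43.87, so 44 per arm: reproduced. The trial randomises 198 (99 per arm).

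**2. How often a low record occurs.** Assume Poisson counts over 72 hours with mean 3 × daily rate. P(0) = exp(−3 × rate).

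| True rate per day | P(0) | P(0 to 2) |
|---|---|---|
| 1 | 5.0% | 42% |
| 2 | 0.25% | 6.2% |
| 3 | 0.01% | 0.6% |

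The documents give no distribution of rates. Assumed here: lognormal, median 1.8, 2.5 or 3.5 per day, log-SD 0.6, cut at 1 or 0.5 per day. Expected zero records are then 0.3 to 3.5 of 158 women, or 0.4 to 4.4 of 198. Records of one or two episodes number 5 to 25 of 158. (158 is the synopsis figure for I-QOL before its addition of 40.)

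A harsher case: every woman at exactly 1 per day, with strongly overdispersed counts (negative binomial, k = 2). P(0) is then 16%, or about 32 of 198.

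**3. Effect on the sample size.** Take 158 evaluable women. Removing 4 leaves 154. In the harsher case 158 × 0.16 ≈ 25 are removed and 133 remain. Both exceed the 88 required.

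**4. Effect on power and type I error.** Assumed: control rate × 0.9, individual change log-SD 0.5, 79 per arm, zero baselines left out. At app × 0.45 (a 45-point difference), the planned ANCOVA has simulated power of about 97 to 99%. With both arms × 0.9, its simulated type I error is 0.048.

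**5. Effect on the estimate.** For baseline count Y with mean λ, the mean observed ratio exceeds the ratio of underlying rates by the factor λ·E[1/Y | Y ≥ 1]. This is 1.30, 1.25 and 1.15 at 1, 2 and 3 episodes per day, and 1.14 to 1.22 over the assumed mixes. It applies to both arms:

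- Difference: 45 × 1.14 = 51 to 45 × 1.22 = 55 points. With at least three baseline episodes it is 46 to 49.
- App arm's own reduction: 1 − 0.45 × 1.14 = 49% down to 1 − 0.45 × 1.22 = 45%, against 55% on the underlying rates.

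So the between-arm difference is enlarged while the app arm's own reduction is understated.

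**6. The passages together.** The threshold is in episodes per day, the same unit as IEF. The record is due in the column that holds the criteria check, before randomisation. Post-consent ineligibility leads to screening failure. A centre that follows all three would not randomise a woman whose record shows no episodes.

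**The case for a change.** The strongest case for a change is that none of these passages requires the check. Compatibility is not an instruction, and the unseen SAP may contain no rule for zero. Under the assumptions above, the chance of at least one zero baseline among 198 women is 34% to 99%, so the question could well arise. The Wilcoxon test limits the influence of extreme ratios but gives no value at zero and does not alter the estimated mean. A true 45-point difference would on average be reported as above the aim in section 8.6, "desired reduction of the mean relative IEF by 50% versus control". At a smaller effect (app × 0.65), ANCOVA power at 79 per arm is 49 to 68%, against 68 to 77% with an entry check.

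The silence of the text stands. The rest carries less weight:

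- The enlarged estimate is an error only against a ratio of underlying rates that the plan never names. The endpoint is defined as the observed change divided by the observed baseline, and ANCOVA estimates its mean difference.
- The 50% is an aim. The hypothesis tested in section 8.8 is equality of the arms, so crossing 50% decides nothing.
- App × 0.65 is a 25-point difference, half the planned effect. The FAS has 99 per arm, not 79; at 99, ignoring imputation, ANCOVA power is 60 to 76% and Wilcoxon power 73 to 88%.
- An entry check would now reach few or no women: recruitment was to end on 31.10.2024 and version 2.1 is dated 14.11.2024.
- Extra analyses, such as ANCOVA in women with at least three baseline episodes or a log-link count model, would be sensitivity analyses. They leave the primary result as it is, and the second estimates a different measure.

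**Conclusion.** No change follows. The plan leaves out a detail that its analysts can settle sensibly in the SAP announced in section 8.12. A woman with a zero baseline has no relative change, so she is not evaluable for endpoints 1 and 14 and remains in everything else. Because the baseline precedes randomisation, this handling is independent of arm and does not bias the comparison.

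The likely size is about 0.3 to 3.5 of 158 women, up to about 4.4 of 198, if counts are Poisson and rates follow the assumed mixes. Marked overdispersion at rates near the threshold would raise this, but even the harsher case leaves 133 evaluable women against 88 needed. The sample size, the type I error and the power at the planned effect stand. The influence of very low baselines on the mean ratio belongs to a relative-change endpoint. It acts on both arms, and the planned Wilcoxon analysis shows whether the test result depends on a few extreme ratios. The low-baseline counts and simulated results rest on rate assumptions that the documents neither give nor contradict; the absence of a written rule rests on none.

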
Treatments/procedures Treatment plan (incl. aftercare):
	
The digital therapy to be tested via app contains the following components:
 
 
● Micturition diary
 
● Pelvic floor training and physiotherapy exercises
 
● Bladder training / cognitive behavioural therapy
 
● Mental exercises             
 
○ Mindfulness
 
○ Progressive muscle relaxation (PMR)
 
○ Stimulus control methods
 
 
 
● Acute urge control
 
● Knowledge section / Nutrition section
 
● Progress tracking and motivation
 
 
The therapy instructions are available at via a smartphone. /tablet-based app in the form of audio, video and text. The medical benefit is assessed via self-reported data points and validated questionnaires from the baseline survey compared to the end of the survey after 12 weeks.

Timetable (duration of study):
	
Patient-centred:
 
Duration of study-related measures: 12 weeks
 
follow-up period: 12 months
 
Study-related:
 
Recruitment phase: 01.04.2024 to 31.10.2024
 
Start date: 01.04.2024
 
Treatment duration: 12 weeks
 
End of study: 15.02.2025
 
Final report: 15.04.2025

Test centres:
	
Clinic and Polyclinic for Urology and Paediatric Urology University Medicine Johannes Gutenberg University Mainz [name]

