### 5.1 Incontinence episodes frequency (IEF)

To increase the accuracy of the results, the incontinence episodes are recorded over a period of 72 hours and an average is calculated over 24 hours [12]. This average value per 24 hours is used as the IEF for the assessment of the primary endpoint. The aim is a relative reduction in incontinence episodes (rel-CfB-IEF) of 50% in the app group compared to the control group.

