## 6.9 Treatment phase

During the treatment phase, the patient is required to log into the Mictera app regularly and carry out the activities described for the day in question. Compliance with the set therapy goals is monitored via the Mictera app in pseudonymised form and reminders are communicated to the patient if necessary. The activity of app use is automatically documented.

The therapy is based on the principle of digital content, which includes personalised multimodal therapy with a focus on pelvic floor training, physiotherapy, mental training and

Kranus Health GmbH\_DINKS

behavioural therapy with methods of urinary urgency control and relaxation techniques. Another key component is the micturition diary, which patients can use to document their micturition behaviour. The approach includes several therapy programme elements whose effectiveness in the treatment of incontinence has been proven in the literature.

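### Micturition frequency, bladder capacity and (by assumption) urgency are planned as between-arm changes from baseline, but no pre-randomisation diary value is described and section 6.8 names only intervention patients for the diary

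*Combined protocol and SAP*

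**What the plan says.** The synopsis (section 1.4) defines endpoints (7), (8), (10) and (11) as changes from baseline to week 12. Section 8.8 analyses continuous endpoints on their changes from baseline, by analogy with the primary ANCOVA (treatment group plus baseline covariate). Endpoints outside the ordered tests (1)–(4) are descriptive, with p-values and 95% CIs.

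On data collection, section 6.8 gives a sequence. After consent and inclusion, "All patients record their incontinence episodes over a period of three days (3 x 24 h"). An unitemised baseline data collection follows, then randomisation. The section then adds: "Furthermore, the intervention patients fill out a micturition diary in the app to record micturition frequency, drinking volume and other symptoms".

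In Table 1 (section 1.5), randomisation is marked under Baseline/V1. The diary row is empty up to and including that column. Its first mark, "X (ongoing documentation possible"), stands in the next column, headed "Onboarding IG/ after study inclusion". A separate row, "Incontinence documentation over 72h", is marked at Inclusion and at week 12.

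The diary is also part of the treatment. It heads the list in the synopsis under "The digital therapy to be tested via app contains the following components", and section 6.9 says: "Another key component is the micturition diary, which patients can use to document their micturition behaviour". Section 3.2 gives controls no access to the app-based intervention for the 12 weeks.

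**The concern.** A between-arm change from baseline needs a start value in both arms, taken the same way and before allocation can influence it. For these endpoints the described instrument is named for one arm only, and its first scheduled use appears to follow randomisation.

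If only intervention patients have diary data, the planned comparison cannot be formed. What remains is a within-arm change in app users, which should not carry a between-arm p-value. If both arms keep a diary from onboarding, the comparison can be formed, but it is adjusted for a post-randomisation value that may already hold some treatment effect.

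The stake is limited to descriptive secondary endpoints. The synopsis does, however, list these reductions and the gain in bladder capacity among the objectives of a superiority study, so the between-arm results are likely to be read as supporting evidence.

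**Working it through.** **1. From endpoint to instrument.** Section 6.9.1 says the diary can hold intake, meals, voided amount and frequency, and symptoms.

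- (7), (8) frequency by day and night: diary.
- (11) functional bladder capacity: diary, from voided amounts.
- (10) imperative urge: diary only on the assumption that urgency is logged under symptoms. Question 2 of the S/U-IQ counts urge episodes with leakage, not urgency as such.

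The appended questionnaires and the week-1 questions in section 5.2.6 contain no day or night micturition frequency and no bladder capacity. Section 8.12 names two data sources, the app and an ePRO system, and describes the ePRO for the questionnaires.

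**2. Timing and arm.** Counting the columns of Table 1 as extracted:

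- Randomisation: column 3.
- Diary: columns 4, 6, 7, 8, 9, 10 and 11.
- 72-hour incontinence record: columns 2, 7, 9, 10 and 11.

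The diary row has no arm label, whereas the technical-support marks at onboarding and week 2 are labelled for the intervention group. Section 6.8 names only intervention patients, in the app, after describing randomisation.

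**3. Content of the shared record.** Section 5.1 says of it: "the incontinence episodes are recorded over a period of 72 hours and an average is calculated over 24 hours". Sections 5.1 and 6.8 mention no voids, volumes or urgency for this record.

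**4. What can be compared.**

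- Diary in the intervention arm only: no control baseline, so no between-arm change.
- Diary in both arms from column 4: a change can be formed from a post-randomisation start value.
- Week-12 values in both arms: a valid randomised comparison without baseline adjustment.

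**5. Possible bias with a post-randomisation start value.** Let D be the week-12 effect, f the share of D already present in the start value and r the within-arm correlation between start and week 12, with equal SDs. The ANCOVA slope is then r, so

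estimate = D − r × (f × D) = D × (1 − r × f).

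- f = 0: factor 1, no bias.
- f = 0.1, r = 0.3: 1 − 0.03 = 0.97, 3% too small.
- f = 0.2, r = 0.7: 1 − 0.14 = 0.86, 14% too small.

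The documents give neither f nor r; these values are assumptions.

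**6. Price of using week-12 values only.** Relative to ANCOVA with a true baseline, the CI width ratio is 1/√(1 − r²):

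- r = 0.3: 1/√0.91 = 1.05.
- r = 0.5: 1/√0.75 = 1.15.
- r = 0.7: 1/√0.51 = 1.40.

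**The case against.** The strongest reply is that the 72-hour record may itself be a three-day voiding diary. Section 4.3 describes a three-day micturition diary averaged to 24 hours. Section 5.1 introduces the study's record in nearly the same words and cites the same reference [12], whose title concerns voiding diaries. If the record is that diary, a pre-randomisation value exists in both arms. This is possible but not stated: section 4.3 is general background, sections 5.1 and 6.8 describe incontinence episodes only, and Table 1 keeps the two records in separate rows.

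Three further points stand in part. The baseline data collection in section 6.8 is not itemised and could include these items. Section 6.8 does not say that only intervention patients keep a diary, although no tool outside the app is described for controls. And for any control-arm diary, the post-randomisation timing rests on column order: the header speaks of study inclusion, which section 6.8 places at consent, before randomisation.

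A reader might infer that controls have no diary data, or that a baseline is certainly missing. The documents do not support that. They show what is described, not what was collected.

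**Conclusion.** The point holds as a gap between the planned analysis and the described data collection. Followed as written, the comparison for (7), (8) and (11), and for (10) under the stated assumption, either has no control baseline or uses a post-randomisation start value that comes from a treatment component in the intervention arm. That is four of the fifteen secondary endpoints, or three without (10).

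A reader might take 3–14% as the expected bias. It is not an estimate. It follows from assumed shares of 10–20% and correlations of 0.3–0.7, and the bias is zero if the start value carries no effect. The documents do not allow it to be quantified.

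The primary endpoint, the ordered tests (1)–(4), power and the sample size of 198 are unaffected. The matter should be settled before analysis because between-arm p-values are planned.

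**What to change.** 1. Reconcile section 6.8 with the diary row of Table 1. For (7), (8), (10) and (11), state instrument, arm and time point. Do the same for pad use (9), which has no named instrument, and for week-12 weight (12), since section 5.2.6 asks for weight in week 1 only.

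2. In the detailed SAP that section 8.12 announces, fix this rule before the analysis:
   - Use the baseline-adjusted comparison only if pre-randomisation values were collected by the same method in both arms for the analysed population.
   - Otherwise compare week-12 values, if both arms have them.
   - Otherwise describe the intervention arm and drop the between-arm p-values.

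Neither step needs new data. The downside is precision: with week-12 values only, CIs are about 5–40% wider than with a true baseline at assumed correlations of 0.3–0.7.

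The repair should not rely on collecting new baselines. Planned recruitment ended on 31.10.2024 (section 6.3), 14 days before version 2.1 of 14.11.2024, so few or no patients are likely to remain to be randomised.
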